6 STUDY TREATMENT(S)

6.1 Description of Treatment(s)

6.1.1 Study Drug

Recombinant human heparin N-sulfatase (rhHNS) drug product formulation is a sterile solution for injection in single-use vials for intrathecal (IT) administration. It is formulated in an aqueous isotonic solution containing 15.0 mg/mL rhHNS in 145 mM sodium chloride, 0.005% (v/v) polysorbate 20, 5 mM sodium phosphate at pH 7.0.

6.1.2 Placebo or Control

This study will not employ a placebo or control.

6.2 Treatment(s) Administered

rhHNS for IT administration will be provided by Shire HGT. rhHNS will be administered by an IDDD. Following the review and signing of informed consent, patients will receive the same dose of rhHNS they received in Study HGT-SAN-055:

- Group 1: rhHNS administered by IT injection 10 mg once per month
- Group 2: rhHNS administered by IT injection 45 mg once per month
- Group 3: rhHNS administered by IT injection 45 mg every other week (EOW)

6.3 Selection and Timing of Dose for Each Subject

The patient's dose of rhHNS will be the same dose (10 mg and 45 mg once per month and 45 mg EOW) they received in Study HGT-SAN-055. Patients will check in to the study center 1 day prior to intrathecal rhHNS dosing for safety assessments on each rhHNS treatment week, and if no safety concerns exist, will subsequently receive IT administration of rhHNS on Day 2. Patients will be discharged from the inpatient unit a minimum of 1 day following dosing with rhHNS and when deemed clinically stable by the Investigator.

The IT injections are to be administered 28 days (± 7 days [groups 1 and 2]) and 14 days (± 3 days [group 3]) apart. If a patient's IDDD becomes nonfunctional, it will be replaced so that the patient can remain on study. See [Section 6.5](#) for a description on the replacement of a nonfunctional IDDD.

6.4 Cerebral Spinal Fluid Sample Procedure

A total of 10 mL of CSF will be obtained in two 5 mL aliquots prior to each injection for safety evaluation using the IDDD. A topical anesthetic agent may be applied over the skin covering the IDDD reservoir prior to CSF sampling. However, CSF will not be obtained if use of the IDDD is precluded, with the exception at the EOS visit, when it may be obtained by means of a lumbar puncture (LP). The performance of LP is at the discretion of the Investigator. An intracranial pressure (ICP) measurement will be obtained whenever a LP is performed.

If a lumbar puncture is to be performed, the patient will be anesthetized via general anesthesia with appropriate airway management. Once the patient is anesthetized, a lumbar puncture will be performed and a CSF sample will be obtained.

6.5 Intrathecal Administration of rhHNS

rhHNS will be administered using an IDDD. After appropriate pre-procedure assessments are completed, anesthesia cream will be applied to the skin over the port. Patients may receive mild sedation to alleviate anxiety and/or to facilitate drug delivery.

Patients will then receive their appropriate dose of rhHNS via slow push/ injection over 2 to 5 minutes. Replacement of fluid, including drug, to the CSF will be an approximate equal volume to that removed. The patient's vital signs will be continuously monitored. The patient will also be monitored closely during enzyme administration and through the next 24 hours for any adverse clinical reactions. The patient will be encouraged to lie down comfortably for 1 to 3 hours post injection, although this may be difficult for the most hyperactive patients.

If use of the IDDD is precluded on a scheduled day of dosing, the IDDD will be declared a failure; no study drug will be administered, nor CSF sample obtained on that visit. Unlike the HGT-SAN-055 study, no study drug will be administered by lumbar puncture in this extension study. Upon declaration of failure, the IDDD will be removed and the patient scheduled for re-implantation of a new IDDD (see [Section 7.11](#)) at the earliest convenience, so that the patient may remain on, or remain as close as possible, to his/her original IT rhHNS dosing schedule. Note: Patients will require 1 week of recovery time from time of re-implantation, during which time the IDDD cannot be used, this may result in a delay in the next scheduled dose of rhHNS. The patient will resume his or her original dosing schedule; no catch-up dosing will occur.

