7.11 Surgical Re-implantation of the IDDD

If a patient's IDDD becomes nonfunctional or infected, it will be replaced so that the patient can remain on study. Procedures for implantation will be detailed in the device's Instructions for Use manual. The patient will be under general anesthesia for this procedure. Standard hospital procedure for surgery will be followed and will include an X-ray to confirm device placement at the mid-thoracic level. A post-operative check of the IDDD will be performed on Day 7 following surgery. X-rays may be performed to check placement of the device, as needed, throughout the study. Drug can only be administered via the IDDD.

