Appendix 1 Schedule of Events

Table 1 Study Assessments for Patients Who Have Received 6 Months of Treatment With rhHNS (Study HGT-SAN-055) (Dose Groups 1 and 2)

Assessment	Screening/ Baseline Visit ⁱ	Week 1 Each Treatment Month			12, 24, 36, and 48 months	End of Study ^f	Safety Follow-up ^h
		Pre-Tx Day 1 ^{a,1}	IT administration Day 2	Day 3 ^d			
Informed Consent/Enrollment		•					
Physical Examination	•	•	•			•	
Height and Weight	•	•				•	
Head Circumference	•				•	•	
Visual and Hearing Assessment					•	•	
ECG	•		• ^b			•	
Vital Signs	•	•	•	•		•	
Hematology	•	•				•	
Serum Chemistry	•	•				•	
Urinalysis	•	•				•	
Urine Heparan Sulfate and Heparan Sulfate Derivatives	•				• ^c	•	
Serum Heparan Sulfate and Heparan Sulfate Derivatives	•				• ^c	•	
Anti-rhHNS antibody testing (serum and CSF) ^j	•				•	•	
Auditory Brainstem Response (ABR)	•				•	•	
MRI of the Head	•				•	•	
CSF Sample Collection ^k	•		• ^c			• ^c	
rhHNS administration ^g			•				
Neurological Examination	•	•	•	•		•	
Full Neurodevelopmental Testing	•				•	•	
Children's Sleep Habits Rating Scale	•				•	•	
Child Health Questionnaire-50	•				•	•	
Child Health Questionnaire-87	•				•	•	
Infant Toddler QOL Questionnaire	•				•	•	

Table 1 Study Assessments for Patients Who Have Received 6 Months of Treatment With rhHNS (Study HGT-SAN-055) (Dose Groups 1 and 2)

Assessment	Screening/ Baseline Visit ⁱ	Week 1 Each Treatment Month			12, 24, 36, and 48 months	End of Study ^f	Safety Follow-up ^h
		Pre-Tx Day 1 ^{a,1}	IT administration Day 2	Day 3 ^d			
Concomitant Medications, Therapies, and Procedures	•	•	•	•		•	•
Adverse Event Monitoring	•	•	•	•		•	•

Abbreviations: ABR = Auditory brainstem response; CSF = cerebrospinal fluid; ECG = electrocardiogram; MRI = Magnetic resonance imaging;
 TX = treatment;

^a Week 1 only, and only performed if >7 days have elapsed since HGT-SAN-055 EOS visit assessments.

^b ECG to be performed following administration of study drug.

^c A total of 10 mLs of CSF will be obtained in two 5 mL aliquots (labeled separately – process according to study operations manual). An attempt will be made to obtain CSF sample via the IDDD prior to each administration of rhHNS and at the End of Study visit. If it is not possible to obtain CSF using the IDDD, the IDDD will be replaced. See [Section 6.4](#) for details.

^d Patients will be discharged when deemed clinically stable by the Investigator.

^e Specimens collected once a month, at Day 1 of the first treatment week.

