Fibrosis-cosmesis	Fibrosis-cosmesis	Visible only on close examination	Readily apparent but not disfiguring	Significant disfigurement; operative intervention indicated if patient chooses	—	—

MUSCULOSKELETAL/SOFT TISSUE

Page 2 of 4

		Grade				
Adverse Event	Short Name	1	2	3	4	5
Fibrosis-deep connective tissue	Fibrosis-deep connective tissue	Increased density, "spongy" feel	Increased density with firmness or tethering	Increased density with fixation of tissue; operative intervention indicated; interfering with ADL	Life-threatening; disabling; loss of limb; interfering with vital organ function	Death
ALSO CONSIDER: Induration/fibrosis (skin and subcutaneous tissue); Muscle weakness, generalized or specific area (not due to neuropathy) – Select ; Neuropathy: motor; Neuropathy: sensory.						
Fracture	Fracture	Asymptomatic, radiographic findings only (e.g., asymptomatic rib fracture on plain x-ray, pelvic insufficiency fracture on MRI, etc.)	Symptomatic but non-displaced; immobilization indicated	Symptomatic and displaced or open wound with bone exposure; operative intervention indicated	Disabling; amputation indicated	Death
Joint-effusion	Joint-effusion	Asymptomatic, clinical or radiographic findings only	Symptomatic; interfering with function but not interfering with ADL	Symptomatic and interfering with ADL	Disabling	Death
ALSO CONSIDER: Arthritis (non-septic).						
Joint-function ⁵	Joint-function	Stiffness interfering with athletic activity; ≤25% loss of range of motion (ROM)	Stiffness interfering with function but not interfering with ADL; >25 – 50% decrease in ROM	Stiffness interfering with ADL; >50 – 75% decrease in ROM	Fixed or non-functional joint (arthrodesis); >75% decrease in ROM	—
ALSO CONSIDER: Arthritis (non-septic).						
Local complication – device/prosthesis-related	Device/prosthesis	Asymptomatic	Symptomatic, but not interfering with ADL; local wound care; medical intervention indicated	Symptomatic, interfering with ADL; operative intervention indicated (e.g., hardware/device replacement or removal, reconstruction)	Life-threatening; disabling; loss of limb or organ	Death
Lumbar spine-range of motion	Lumbar spine ROM	Stiffness and difficulty bending to the floor to pick up a very light object but able to do activity	Some lumbar spine flexion but requires a reaching aid to pick up a very light object from the floor	Ankylosed/fused over multiple segments with no L-spine flexion (i.e., unable to reach to floor to pick up a very light	—	—

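### The passages on IDDD failure and replacement set different conditions and conflict at End of Study, and device events need a per-access summary because Group 3 has about twice the access days

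*Protocol*

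**What the plan says.** All references are to the Amendment 1 text.

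- **Sections 4.1 and 6.5** (also the synopsis): "If use of the IDDD is precluded on a scheduled day of dosing, the IDDD will be declared a failure". The consequence in 6.5 is: "Upon declaration of failure, the IDDD will be removed and the patient scheduled for re-implantation of a new IDDD". The term precluded is not defined.
- **Section 7.11**, echoed in 4.1 and Appendix 1 footnote g: the device is replaced if it "becomes nonfunctional or infected, it will be replaced so that the patient can remain on study".
- **Section 6.3** refers to a nonfunctional device only, without infection, and sends the reader to 6.5 "for a description on the replacement of a nonfunctional IDDD".
- **Appendix 1, footnote c** (Tables 1 and 2): "If it is not possible to obtain CSF using the IDDD, the IDDD will be replaced". The footnote covers the sample before each administration and the End of Study sample, and it cites Section 6.4 for details.
- **Sections 6.4 and 7.7.4** contain no replacement rule. They say CSF is not collected when the device cannot be used, except that a lumbar puncture may be done at End of Study at the investigator's discretion.
- **Section 8.3** requires the device to be removed at study completion.
- **Section 10.6.1.1** summarizes adverse events judged probably or possibly device-related by dose group and overall.

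**The concern.** The same finding in a child can lead to different actions depending on which passage is read. The action is an operation under general anesthesia (7.11). By 6.5 it is followed by a week in which the device cannot be used, and missed doses are not made up. So the wording affects surgery and exposure as well as labelling.

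It also reaches the safety tables. The primary objective is long-term safety of treatment given through a surgically implanted device, and device-related events are tabulated by dose group. In the CTCAE text appended to the protocol, the Grade 3 entry for local device complications includes "operative intervention indicated (e.g., hardware/device replacement or removal, reconstruction", so whether an operation takes place can bear on the recorded grade.

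Separately, the groups differ in how often the device is accessed. A table of patients with a device event by dose group mixes the dose with the number of occasions on which an event could occur.

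**Working it through.** **1. The conditions applied to the same cases**

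| Case | 4.1 / 6.5 (use precluded on a dosing day) | 7.11 / footnote g (nonfunctional or infected) | Footnote c (no CSF obtainable) |
|---|---|---|---|
| Infection found between dosing days | Not met by its wording | Met (6.3 does not name infection) | Not met |
| Passing obstacle to use on one dosing day | Met on a literal reading | Not clearly met | Met only if CSF sampling fails |
| Device accepts an injection but yields no CSF | Depends on the meaning of precluded | Depends on the meaning of nonfunctional | Met |
| No CSF at the End of Study visit | Not a dosing day | Depends on the meaning of nonfunctional | Met: replace |

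The last row is the sharpest conflict. Footnote c says replace, 6.4 and 7.7.4 allow a lumbar puncture instead, and 8.3 has the device removed. The section that footnote c cites does not contain the rule the footnote states.

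**2. Access days per patient**

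Inputs: 10 mL of CSF per access (6.4); approximate maximum total CSF of 480 mL for Groups 1 and 2 and 960 mL for Group 3 (Table 7-1).

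- 480 / 10 = 48 and 960 / 10 = 96.
- Check: 1 access × 48 months × 10 mL = 480 mL, and 2 × 48 × 10 mL = 960 mL. Table 7-1 is reproduced.
- Counting only the extension: 48 − 6 = 42 months, giving 42 and 84.
- By the 28- and 14-day intervals over 3.5 years (1,278 days): about 46 and 91. Over 4 years (1,461 days): about 52 and 104.

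The ratio is 2:1 on every count.

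**3. What the ratio does to a per-patient table**

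The documents give no per-access probability of an event, so *p* is an assumption shown over a range, with access days taken as independent. Expected events per patient = *n* × *p*; chance of at least one = 1 − (1 − *p*)^*n*.

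| Assumed *p* | 48 access days | 96 access days |
|---|---|---|
| 0.5% | 0.24 expected; 21% | 0.48 expected; 38% |
| 1% | 0.48 expected; 38% | 0.96 expected; 62% |
| 2% | 0.96 expected; 62% | 1.92 expected; 86% |

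With 42 and 84 access days and *p* = 1%, the chances are 34% and 57%. If failed CSF sampling alone added replacements at a further assumed 1% per access, expected replacements at 48 and 96 access days would rise from 0.48 to 0.96 and from 0.96 to 1.92. These figures show direction and scale only. The 2:1 ratio is the one quantity that does not depend on *p*.

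**The case against.** The passages are linked. Section 4.1 places the nonfunctional-or-infected wording and the precluded wording in one paragraph; 6.3, 7.13 and footnote g point to 6.5; and 6.5 points to 7.11. A fair reading is that 6.5 says what happens when the device does not work and 7.11 describes the surgery. Section 7.11 also gives a sufficient condition for replacement and does not exclude others. Since CSF is drawn through the device before each injection and fluid is replaced in roughly equal volume, aspiration can be seen as part of use, which brings footnote c closer to 6.5 on dosing days. This stands. It narrows the disagreement on dosing days, but it does not define precluded and does not touch the End of Study conflict.

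Several stronger readings are tempting, and the documents do not support them:

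- A reader might infer that 6.5 declares failure whatever the reason. The text does not say so. Section 7.7.4 speaks of blockage and mechanical complications, and dosing has a separate check for safety concerns.
- A reader might set a positive failure rate under 6.5 against zero under 7.11. The zero would come from assuming no device fault, so the contrast is circular.
- A reader might hold the single-day rule against the dosing windows in 6.3 ("The IT injections are to be administered 28 days", with a tolerance). Those windows govern spacing and do not contradict 6.5; whether a later attempt should count is a clinical matter.
- A reader might conclude that device results are not comparable across sites. Nothing shows that sites follow different passages.

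Device failure is not a named endpoint, and only 4.1, 6.5 and the synopsis use the word failure. The effect on surgery is therefore direct, while the effect on reported counts runs through device-related adverse events. The SAP, the eCRF and the amendments after Amendment 1 are not available, and any of them may already settle part of this.

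**Conclusion.** The point holds as an inconsistency that should be corrected. It does not invalidate the safety analysis. Three things are established from the text: the condition in 4.1 and 6.5 rests on an undefined term; 6.3, 7.11 and footnote c describe different conditions for replacement; and footnote c, followed literally at End of Study, conflicts with 6.4, 7.7.4 and 8.3 and cites a section without the rule.

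The reporting point rests on the 2:1 ratio of access days, which follows from the regimens under any definition of failure. At an equal per-access probability, Group 3 is expected to have twice the device events per patient for that reason alone. The percentages in the working depend on assumed probabilities and independence and should not be quoted as predictions. No view is taken on which clinical trigger is right.

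**What to change.** Reconcile Sections 4.1, 6.3, 6.4, 6.5, 7.11 and 8.3 and Appendix 1 footnotes c and g to one definition of device failure and replacement, with 7.7.4 kept in line. State what precluded means and what applies at End of Study. The clinical content is for the sponsor to settle.

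Record on the eCRF the reason for each scheduled day on which access was precluded. Report device-related events per access attempt as well as per patient, by dose group.

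The cost is amendment wording, one eCRF field and one extra table.

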6.6 Method of Assigning Subjects to Treatment Groups

This is an open-label, non-randomized study; all patients enrolled in this study will be treated with rhHNS. Patients will remain in the groups (1, 2, or 3) they were assigned to in Study HGT-SAN-055.

6.7 Blinding

Not applicable; this trial is not blinded.

6.8 Concomitant Therapy

All non-protocol treatments and procedures that occur from the time of informed consent (or assent, if applicable) through the safety follow-up contact are regarded as concomitant and will be documented on the appropriate pages of the electronic case report form (eCRF). Concomitant therapy includes medications, therapies/interventions administered to patients, and medical/surgical procedures performed on the patients.

Every effort should be made to keep the patient's symptomatic Sanfilippo syndrome Type A treatment constant throughout the study. However, changes in medications are acceptable if necessary according to clinical judgment. All changes will be recorded on the appropriate eCRF. Concomitant medication will be coded using World Health Organization Drug Reference List (WHODRL).

6.9 Restrictions

6.9.1 Prior Therapy

Prior therapy excluded for this study consists of the following:

- Psychotropic or other medications, which in the Investigator's opinion, would be likely to substantially confound test results and the dose and regimen of which cannot be kept constant throughout the study.
- The patient cannot sustain absence from aspirin, non-steroidal medications, or medications that affect blood clotting within 1 week prior to a relevant study related procedure (eg, device implantation if applicable) or medications within 1 week before any procedures in which any change in clotting activity would be deleterious.
- The patient has received any investigational drug or device intended as a treatment for MPS IIIA within the 30 days prior to the study other than rhHNS or is enrolled in another study that involves an investigational drug or device.
- Hematopoietic stem cell or bone marrow transplant.

6.9.2 Fluid and Food Intake

Oral food and fluid intake are not restricted over the course of the study, with the exception of hospital standard pre-anesthesia dietary restrictions.

6.9.3 Subject Activity Restrictions

There are no restrictions on patient activities in this study.

6.10 Treatment Compliance

rhHNS is administered under controlled conditions by the Investigator; therefore, full patient compliance with study treatment is anticipated in this study.

6.11 Packaging and Labeling

Drug product will be supplied in a 3 mL clear, colorless glass (Type 1) vial. Each vial holds an extractable volume of 1 mL of rhHNS. The closure is a gray, 13 mm stopper composed of butyl rubber with a fluoro resin lamination. The overseal is an aluminum seal with a flip-off, plastic, tamper evident cap.

6.12 Storage and Accountability

Drug product should be stored refrigerated (2 to 8°C); drug product may not be stored beyond the expiration date on the vial.

6.13 Investigational Product Retention at Study Site

All rhHNS study drug delivered to an Investigator will be recorded and accounted for throughout the study. All rhHNS study drug must be recorded on a patient-by-patient basis. The lot number of the IDDD and the date and time of administration of the study medication will be documented on the appropriate eCRF.

All unused study medication and other study materials are to be returned to the Sponsor or its designee or disposed after Sponsor approval per site policy after the study has been completed.

7 STUDY PROCEDURES

7.1 Informed Consent

Study procedures will be conducted only after written informed consent for the patient to participate in this study is provided by the parent(s) or legal guardian(s) and assent from the patient (if applicable). Detailed descriptions of patient evaluations required for this protocol are described in this section. These evaluations will be performed during the indicated days and weeks of each study month (see [Appendix 1](#) Schedule of Events).

All data collected are to be recorded on the appropriate eCRF. The approximate maximum total blood, urine, and CSF volumes to be collected from each patient by the end of this study for safety assessments are presented in Table 7-1.

Table 7-1 Approximate Total Sample Volumes Collected Over the Duration of the Study From Each Patient by Group and Assay

	Groups 1 and 2	Group 3
Blood	290 mL	555 mL
Urine	530 mL	1,010 mL
CSF	480 mL	960 mL

Blood, urine and CSF volumes to be collected for each clinical laboratory measurement are described in detail in the Laboratory and/or Study Operations Manual.

7.2 Physical Examination

A physical examination of each patient will be performed as detailed in [Appendix 1](#) Schedule of Events.

Note: if the patient's hearing cannot be assessed during the physical examination, the patient will have an Ears, Nose, and Throat Evaluation performed under anesthesia at the baseline visit. If it is determined that the patient requires pressure-equalization (PE) tubes, they may be implanted during that same visit. See [Section 7.9](#) for details. Note: Pressure-equalization tubes may be re-implanted if they fall out during this study.

The physical examination findings will be recorded on the eCRF and will include a review of the patient's general appearance as well as the following evaluations:

- Head and neck
- Eyes, ears, nose and throat
- Chest and lungs
- Cardiovascular
- Abdomen
- Skin
- Lymphatic
- Musculoskeletal
- Neurological
- Endocrine
- Genitourinary

